HRP-503B – BIOMEDICAL RESEARCH PROTOCOL (2017-1)

Protocol Title: Preliminary Effectiveness of Remotely Monitored Blood Alcohol Concentration Device as Treatment Modality

Principal Investigator: [name].

Version Date: June 1, 2020

(If applicable) Clinicaltrials.gov Registration #: NCT04380116

INSTRUCTIONS

This template is intended to help investigators prepare a protocol that includes all of the necessary information needed by the IRB to determine whether a study meets approval criteria. **Read the following instructions before proceeding:**

- 1. Use this protocol template for a PI initiated study that includes direct interactions with research subjects. Additional templates for other types of research protocols are available in the system Library.
- 2. If a section or question does not apply to your research study, type "Not Applicable" underneath.
- 3. Once completed, upload your protocol in the "Basic Information" screen in IRES IRB system.

SECTION I: RESEARCH PLAN

1. **Statement of Purpose:** State the scientific aim(s) of the study, or the hypotheses to be tested. The purpose of the current study is to evaluate the usage and acceptability of the Soberlink's blood alcohol concentration (BAC) unit in collaboration with Aware treatment to assess increased sobriety within patients suffering from alcohol use disorder (AUD).

The specific AIMS will be:

- 1) To determine the effectiveness of Soberlink's ability to increase abstinence
- 2) To evaluate the impact of Soberlink's device on the participant based on their quality of health and sobriety.
- 3) To evaluate the extent to which need for higher levels of follow-up care and treatment is reduced for individuals who have had access to the Soberlink device.
- 2. **Probable Duration of Project:** State the expected duration of the project, including all follow-up and data analysis activities.

The duration of the time of the study will be two years to complete. This will include (as seen on Figure 1) time for IRB approval and recruitment, randomization and completion the study, follow-up and lastly analysis with dissemination.

[figure not shown]

Figure 1: Overview and Timeline

3. **Background:** Describe the background information that led to the plan for this project. Provide references to support the expectation of obtaining useful scientific data.

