Alcohol dependence (AD) has been characterized as a chronic disorder that presents an enduring vulnerability to relapse. Unfortunately, AD treatment is commonly delivered as a series of acute care sessions (Etheridge, Craddock, Dunteman, & Hubbard, 1995; McLellan, Lewis, O'Brien, & Kleber, 2000), which means that individuals seeking treatment often face the challenge of maintaining sobriety upon returning to the same environment where they had struggled with alcohol dependence previous to seeking treatment. Studies have shown that 40%–60% of patients treated for alcohol problems relapse within 3 months, and this rate increases to 70%–80% within 12 months (Bradizza, Stasiewicz, & Paas, 2006; McLellan et al., 2000; Witkiewitz & Marlatt, 2004). medical costs associated with alcohol use disorders (AD) are over \$120 billion per year, until very recently, there has been relatively little involvement of physicians or other general healthcare providers in the treatment of AUDs (Sacks et al., 2015). By convention, most contemporary AUD treatment has been delivered outside mainstream healthcare by specialty "treatment programs" that are time-limited by insurance restrictions and highly structured to deliver a standardized "program" of care (McLellan et al., 2005; Foll et al., 2009).

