4. **Research Plan:** Summarize the study design and research procedures using non-technical language that can be readily understood by someone outside the discipline. **Be sure to distinguish between standard of care vs. research procedures when applicable, and include any flowcharts of visits specifying their individual times and lengths.** Describe the setting in which the research will take place.

Study Sites/Feasibility. The study will be conducted in at clinical office for Aware Recovery Center (North Haven, CT). The census of the facility on average recruits 38 new individuals a month and they currently have 300. This will be the first study, completed at this site, which is a randomized control treatment design.

Procedure:

(www.randomized.com). Individuals will be placed into one of two conditions (Soberlink+Aware; Named Group 1) or (Aware; Named Group 2). Both groups will be consented by either the principal investigator or the research assistants who will be present at all screenings and ensured that they understand their rights. Participants will be told they are allowed to leave or withdraw for the study without penalty or hindering the relationship between themselves and Aware Recovery.

Figure 2: Time Intervals for Assessments

Group 1

This group will include access to the Aware treatment (see 'Aware treatment' below), and access to the Soberlink device. A research assistant will train the participant and provide an orientation (see orientation to Soberlink below) for what will be taught. All participants will be complete screening and outcome assessments, along with using the Soberlink device for the first time. The participant's Soberlink device will be set up to test participants twice a day. Reminder emails (see attached reminder emails) will be sent out the day before, and the day of the 1 month, 2 month and 3-month surveys that will be completed online in the participant's home through a secure link sent directly to them. Subsequent phone calls will be made by the research assistant to the participant if they have missed their evaluation. Upon completion of the surveys, the participants in group 1 will be paid, and reminded of the subsequent follow-ups. The estimated time of the process will take 45 to 60 minutes to complete.

Orientation to Soberlink

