Individuals who miss two consecutive BAC's will be followed up by either Research Assistant or the PI. Individuals who miss four consecutive BAC's without contact of the PI or the research assistant will be temporarily hold unless the individual has expressed thoughts of leaving the study prematurely. Missing more than six consecutive BACs without communication will result in termination from the study by the PI. A pilot study contacted at Aware prior to the PI being involved demonstrated little reactivity or premature departure for those who had access to the Soberlink device.

Aware/Group 2:

This group will not receive access or training to Soberlink device, however they will be recruited to complete the same set of surveys at the same time intervals (See Figure 2). Upon completion of the surveys, the participants in group 2 will be paid, and told reminded the subsequent follow-ups. Reminder emails (see attached reminder emails) will be sent out the day before, and the day of the 1 month, 2 month and 3 month evaluations. Subsequent phone calls will be made by the research assistant to the participant if they have missed their evaluation. The estimated time of the process will take under 30 minutes to complete.

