We are planning to assess a broad range of subject characteristics, process measures and treatment outcomes over the 3-month trial and at the 6 week post treatment follow-up (See Table 1). Baseline assessments are designed to ensure that patients meet eligibility criteria and that important predictor variables such as cognitive impairment are assessed. Baseline measures include evaluation and understanding of the extent of the AUD issue from a several different vantages points. Primary outcome measures include reductions in days per week of use and negative BAU screens for alcohol. Monthly assessments will take approximately 30 minutes and monthly and follow-up's 45 minutes. Patients will be paid \$10 for the baseline and monthly assessments, \$25 for follow-up assessments (up to \$65 total).

active alcohol use disorders.

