Confidentiality with regard to collected materials will be maintained via a numbered reference—system maintained by the principal investigator. Subjects' names will appear only on a consent—form and "key" form kept in a secured cabinet by the PI, separate from the subject records. All collected materials will be kept in locked file cabinets in a secured office. Inclusion and exclusion criteria, and the use of trained clinical interviewers in the assessment phase of the study will help to avoid the acceptance of subjects into this study who have either insignificant substance abuse or significant psychiatric contraindications to both treatments in this study. In cases of psychological deterioration or worsening substance abuse, we will recommend to patients to contact their physician immediately and consider withdrawing from the study to receive more intensive treatments. When necessary subjects will be withdrawn from this study and research staff will assist patients with appropriate sites for treatment such as the care coordinator, their sponsor or the emergency room. In instances of suicidal or homicidal risk, appropriate authorities including their primary provider will be informed and necessary actions (seeking crisis/suicidality evaluations and possible hospitalization) taken. Soberlink have facial recognition to confirm its the correct participant testing, while also have internal sensors and algorithms that can detect if the participant is using an alternative air source (i.e. air pump) or sample is not consistent with human breath.

- 12. **Data and Safety Monitoring Plan:** Include an appropriate Data and Safety Monitoring Plan (DSMP) based on the investigator's risk assessment stated below. (Note: the HIC will make the final determination of the risk to subjects.)
 - a. What is the investigator's assessment of the overall risk level for subjects participating in this study? The risks associated with participating in this study can be categorized as minimal (i.e., risks are commensurate with everyday risks associated with drug abuse treatment and data have adequate protection for maintaining confidentiality).
 - b. If children are involved, what is the investigator's assessment of the overall risk level for the children participating in this study? N/A

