13. **Statistical Considerations:** Describe the statistical analyses that support the study design. A sample size of 110 would provide >80% power (α = .05) to detect a medium to large effect size (d= .65) and allow to fully evaluate gender differences. Greater power is provided by the repeated measures GEE and LMM analysis for the primary outcomes of BAC screen negative for alcohol drugs and days/month of self-reported illicit drug use. Sample size calculations for LMM are dependent on the number of repeated events, the retention rate, and the interclass correlation, in addition to the alpha level, the expected effect size, and the statistical power 198. The current randomized trial would provide estimates to guide a power analysis for a large Stage II study. Statistical procedures and models for analyzing data have been selected according to the research hypotheses being investigated and the types of data available. We will use α < .05, but will use appropriate corrections for multiple tests. Statistical analyses will be conducted on an intention-to-treat sample using SPSS. Using chi square and t-tests, we will first conduct preliminary analyses of the adequacy of the randomization procedure, the comparability of baseline measures for the two groups, and the possible need for covariates in the analyses of treatment outcome data.

SECTION II: RESEARCH INVOLVING DRUGS, BIOLOGICS, RADIOTRACERS, PLACEBOS AND DEVICES

ft
his
section
(or one
of its part
s. A or B
() is not
applicable.
check o
ff N/A
and de
lete the
rest of th
e section.

A.	RADIOTRACERS ⊠N/A	
1.	Name of the radiotracer: Write here	
2.	Is the radiotracer FDA approved? □YES	□NO

- If NO, an FDA issued IND is required for the investigational use unless RDRC assumes oversight.
- 4. **Background Information:** Provide a description of previous human use, known risks, and data addressing dosage(s), interval(s), route(s) of administration, and any other factors that might influence risks. If this is the first time this radiotracer is being administered to humans, include relevant data on animal models.

Check one: □IND# Write here or □RDRC oversight (RDRC approval will be required prior to use)

Write here

3.

4. **Source:** Identify the source of the radiotracer to be used. *Write here*

5. **Storage, Preparation and Use:** Describe the method of storage, preparation, stability information, method of sterilization and method of testing sterility and pyrogenicity.

Write here

R	DRUGS/BIOLOGICS

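### Worsening substance use is a stated route out of the study, and no visible text continues the surveys after a patient leaves

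*Combined protocol and SAP*

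**What the plan says.** Section I, item 11 (Minimizing Risks) names two triggers, psychological deterioration and worsening substance use. For the second it reads "worsening substance abuse, we will recommend to patients to contact their physician immediately", and the same sentence goes on to advise the patient to "consider withdrawing from the study to receive more intensive treatments. When necessary subjects will be withdrawn from this study". After that, staff help the patient find treatment. Data collection is not mentioned.

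Three other places show what is affected:

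- Section I, item 4, Assessments: "Primary outcome measures include reductions in days per week of use and negative BAU screens for alcohol". Group 2 has no device, so self-reported use is the one of these two outcomes that both arms supply.
- Section I, item 1, Aim 3 asks how far the "need for higher levels of follow-up care and treatment is reduced for individuals who have had access to the Soberlink device".
- Section I, item 13: "Statistical analyses will be conducted on an intention-to-treat sample using SPSS". It names GEE and LMM but gives no rule for data after withdrawal.

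For follow-up, the descriptions of both groups in item 4 say "Subsequent phone calls will be made by the research assistant to the participant if they have missed their evaluation".

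**The concern.** Worsening use is both a value of the primary outcome and a written reason to leave the study. A patient who follows the advice is lost to later surveys. If the patient leaves before the current month's survey, the bad month is lost too. The Time Line Follow Back in Table 1 covers the preceding 30 days, so a survey taken more than a month later would not recover it.

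If the worse month is recorded first, the LMM can partly allow for the loss, because the missingness then depends on observed data. If it is not recorded, neither the LMM nor a standard GEE can. The intention-to-treat label defines who is analysed. It does not supply values that were never collected.

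Aim 3 is exposed in the same way. The stated purpose of leaving is more intensive treatment, which is the event Aim 3 sets out to compare. Item 13 also says the trial will supply estimates for a later Stage II power analysis, so a distorted effect would carry forward.

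**Working it through.** **1. Does other text close the gap?**

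| Place | What it provides | What it leaves open |
|---|---|---|
| Item 4, Groups 1 and 2 | Reminder emails and calls for missed evaluations | Not said to apply after withdrawal |
| Item 4, data monitoring after Table 1 | Reports on active subjects and percentage of missing data | Not stated by arm; no reasons; no recovery of values |
| Item 13 | Intention-to-treat sample | No rule for missing or post-withdrawal data |
| Section III, item 6 | Freedom to withdraw | Silent on later data |
| Section IV, item 1 | Admission and discharge dates collected | Not said to continue after withdrawal; no reason recorded |

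None continues the surveys or records the reason for withdrawal by arm.

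**2. The plan's own figure.** With 110 patients (taken as 55 per arm), d = 0.65 and two-sided α = 0.05: 0.65 × √(55/2) − 1.96 = 1.45, so power is about 93% (t-test 92%). The claim of more than 80% holds. The t-test figure is 85% at 20% loss, 80% at 30% and 74% at 40%. Power is not the main issue.

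**3. How many could leave.** The plan gives no withdrawal rate. The Background section says "Studies have shown that 40%–60% of patients treated for alcohol problems relapse within 3 months". Treat relapse as worsening and assume that 10% to 50% of relapses end in withdrawal. Then 110 × 0.40 × 0.10 = 4.4 patients at the low end and 110 × 0.60 × 0.50 = 33 at the high end, which is 30% of the sample.

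**4. Direction of bias.** All inputs here are assumed. Worsening occurs in p = 40% of controls and 20% of device patients. Drinking days per month are 15 if worsened and 3 otherwise. A share w of worsened patients leaves, equally in both arms, and would drink x days in a later month.

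- Mean seen: [15p(1 − w) + 3(1 − p)] / (1 − pw)
- Mean with full follow-up: 15p(1 − w) + xpw + 3(1 − p)

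At w = 50%, the means seen are (3.0 + 1.8)/0.8 = 6.00 and (1.5 + 2.4)/0.9 = 4.33, a difference of 1.67. With full follow-up the difference is (4.8 + 0.2x) − (3.9 + 0.1x) = 0.9 + 0.1x. That is 2.4 if drinking persists (x = 15) and 0.9 if the patient is abstinent in intensive care (x = 0). The two agree at x = (1.67 − 0.9)/0.1, about 7.7 days.

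| w | Difference seen | Full, x = 15 | Full, x = 0 | Error |
|---|---|---|---|---|
| 10% | 7.50 − 5.20 = 2.30 | 2.4 | 7.2 − 5.1 = 2.1 | 4% too small or 9% too large |
| 25% | 7.00 − 4.89 = 2.11 | 2.4 | 6.3 − 4.65 = 1.65 | 12% too small or 28% too large |
| 50% | 6.00 − 4.33 = 1.67 | 2.4 | 4.8 − 3.9 = 0.9 | 31% too small or 85% too large |

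If p is the same in both arms, both differences are zero.

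**5. With a model.** The arithmetic above covers one later month and gives the model no credit for earlier visits. Simulations used a random-intercept LMM over three monthly visits, with relapse halved by the device, equal detection and half of withdrawals before that month's survey. At a 50% withdrawal chance they gave roughly 13% to 23% dilution when drinking persisted. When withdrawn patients were set to zero days, they gave about 20% to 38% overstatement. At a 10% chance, dilution with persistent drinking was 2% to 4%. With equal detection and no true effect, bias was within 0.011 days per month of zero.

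**The case against.** The strongest case against is that this is ordinary safety language. Staff recommend that a patient consider leaving, and the sentence on withdrawal when necessary does not repeat the trigger. That sentence follows directly, so reading it as covering worsening use is natural, but both steps remain advisory or discretionary. The consent form may set terms for data after withdrawal. It is not available here, and its absence is not a fault in the plan.

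The illustration is also generous. The 40% to 60% relapse figure describes treated patients in general, whereas trial patients receive intensive in-home care. The withdrawal chances have no source. The prior pilot "demonstrated little reactivity or premature departure for those who had access to the Soberlink device", which points to the lower end for Group 1 but says nothing about Group 2. These points limit the size of the problem. They do not supply the missing rule.

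Continued surveys also bring a difficulty of their own. Patients in residential care could be scored as abstinent, so the sickest might look like successes. That stands, and the fix has to deal with it.

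A reader might infer that the rule biases the result in favour of the device, because Group 1 relapses would be seen sooner. The documents do not say so. The written response to a positive reading is an automatic retest, and Aware care is described as rigorously monitored for both arms. Under a hypothetical 75% v 25% split in detection before the survey, the simulated bias was 0.07 to 0.81 days per month, in each case below one standard error at 55 per arm.

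**Conclusion.** The point holds as a cheap improvement. Following item 11 as written can remove primary-outcome values because of what those values are, and can remove patients as they reach the Aim 3 event. No visible text prevents this.

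The size cannot be determined, because the plan does not say how often worsening leads to withdrawal or how it is detected in each arm. The direction cannot be determined either. A reader might infer that equal detection with a real effect must dilute the result. That is true only if drinking stays high after withdrawal. If intensive treatment brings it down enough, the analysis overstates the effect. The percentages above rest on assumed inputs and show only that both signs are possible. The case for the change rests on the better rule and its low cost. It is separate from the rule that ends participation after more than six consecutive missed breath tests.

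**What to change.** In Section I, item 11, state that stopping the device, or referral to or entry into more intensive treatment, does not by itself end study participation. Then add:

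- Unless the patient withdraws consent for data collection, the month 1, 2, 3 and 6-week assessments continue in both arms, with the same payments, and enter the intention-to-treat analysis.
- The date of and reason for each treatment change or withdrawal are recorded by arm. This also serves Aim 3.
- Days in a controlled or residential setting are recorded, with a sensitivity analysis that does not count those days as abstinent.
- Clinical referral and crisis steps stay unchanged.

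The cost is protocol wording, plus consent wording only if the consent form says otherwise. The monthly surveys are already online. Payments after baseline are at most 3 × 10 + 25 = 55 USD per patient, so 55 × 4.4 = 242 to 55 × 33 = 1,815 USD in the illustration, all within the planned 65 USD per person. The downside is modest follow-up effort for patients in higher care and one more sensitivity analysis.

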 - c. Include an appropriate Data and Safety Monitoring Plan. Examples of DSMPs are available here http://your.yale.edu/policies-procedures/forms/420-fr-01-data-and-safety-monitoring-plans-templates for
 - i. Minimal risk
 - ii. Greater than minimal
 - d. For multi-site studies for which the Yale PI serves as the lead investigator:
 - i. How will adverse events and unanticipated problems involving risks to subjects or others be reported, reviewed and managed? NA
 - ii. What provisions are in place for management of interim results? NA
 - iii. What will the multi-site process be for protocol modifications? NA

The principal investigator is responsible for monitoring the data, assuring protocol compliance, and conducting the safety reviews at the specified frequency monthly, quarterly. During the review process the principal investigator will evaluate whether the study should continue unchanged, require modification/amendment, or close to enrollment.

The principal investigator, the Institutional Review Board (IRB) have the authority to stop or suspend the study or require modifications.

This protocol presents minimal risks to the subjects and Unanticipated Problems Involving Risks to Subjects or Others (UPIRSOs), including adverse events, are not anticipated. In the unlikely event that such events occur,

Reportable Events (which are events that are serious or life-threatening and unanticipated (or anticipated but occurring with a greater frequency than expected) and possibly, probably, or definitely related) or Unanticipated Problems Involving Risks to Subjects or Others that may require a temporary or permanent interruption of study activities will be reported immediately (if possible), followed by a written report within 5 calendar days of the Principal Investigator becoming aware of the event to the IRB (using the appropriate forms from the website) and any appropriate funding and regulatory agencies. The investigator will apprise fellow investigators and study personnel of all UPIRSOs and adverse events that occur during the conduct of this research project through regular study meetings and/or via email as they are reviewed by the principal investigator. The protocol's research monitor, study sponsors, funding and regulatory agencies will be informed of serious adverse events within 5 days of the event becoming known to the principal investigator.

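### No scheduled adverse-event question is described for either group, and staff contact differs by group, so event counts may be incomplete and not comparable between groups

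*Combined protocol and SAP*

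**What the plan says.** Section I, item 12 says of unanticipated problems: "including adverse events, are not anticipated. In the unlikely event that such events occur", and goes on to reporting. A written report to the IRB follows "within 5 calendar days of the Principal Investigator becoming aware of the event". The PI is responsible for "conducting the safety reviews at the specified frequency monthly, quarterly", and at these reviews "the principal investigator will evaluate whether the study should continue unchanged, require modification/amendment, or close to enrollment". How an event comes to the PI's notice is not described.

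Item 11 (Minimizing Risks) plans for psychological deterioration and worsening substance abuse, with the emergency room among the places to which staff may direct a participant. For suicidal or homicidal risk it has "necessary actions (seeking crisis/suicidality evaluations and possible hospitalization) taken".

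Item 4 (Research Plan) sets the contact in each group. In Group 1, "The participant's Soberlink device will be set up to test participants twice a day", and "Individuals who miss two consecutive BAC's will be followed up by either Research Assistant or the PI". The same paragraph has the PI end participation after more than six consecutive missed tests without communication. Group 2 has no device, but completes the same surveys at the same times. Both groups have this rule: "Subsequent phone calls will be made by the research assistant to the participant if they have missed their evaluation". Table 1 lists the instruments.

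**The concern.** If nobody asks about events on a schedule, the safety review sees only what happens to reach staff. That depends on contact, and contact is not the same in the two groups. Two things are at stake. Serious events could go unrecorded in either group, although the PI's decision to continue, modify or close enrollment draws on them. And if anyone later sets the groups' counts side by side, a difference could reflect how events were found rather than what happened.

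There is also a link to Aim 3 (Section I, item 1), which concerns whether access to the device reduces the need for higher levels of care. Table 1 lists no measure of this. Section IV names admission and discharge dates among the data collected, but does not say admission to what, or how and when the dates are obtained.

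**Working it through.** The documents give no adverse-event figure to reproduce, so the check is mainly a comparison of text.

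**1. Is any method of finding events described?** Item 12 gives who reviews, how fast to report and whom to tell. It gives no question, form or schedule. Table 1 covers anxiety, depression, psychiatric diagnosis, substance use and its history, self-efficacy, breath alcohol, quality of life, opinion of the device, coping responses and an alcohol screen. The Time Line Follow Back looks back 30 days, but at substance use. None is described as recording emergency visits, admissions or other serious events.

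**2. Routes by which study staff could learn of an event**

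| Route or rule | Group 1 | Group 2 |
|---|---|---|
| Surveys at months 1, 2 and 3 | yes | yes |
| Call after a missed evaluation | yes | yes |
| Six-week follow-up | yes | yes |
| Time Line Follow Back, described as research-administered | yes | yes |
| Aware in-home care (not described as a route to the study) | yes | yes |
| Test results visible to PI and research assistant (item 10) | yes | no |
| Staff follow-up after two consecutive missed tests | yes | no |
| Termination after more than six missed tests without communication | yes | no |

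The first five rows are shared and cancel. The last three are the asymmetry.

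**3. How much extra contact?** Scheduled tests: 2 per day × 90 days = 180 per person (2 × 84 = 168 to 2 × 92 = 184). These are not 180 staff contacts. A call needs two misses in a row, 2 ÷ 2 per day = about one day, and a fully adherent participant generates none. Termination applies from the seventh consecutive miss, 7 ÷ 2 = 3.5 days.

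**4. Which direction?** A Group 1 participant who is admitted would probably miss tests, and that can prompt a call within about a day. This raises capture in Group 1. If the participant stays out of contact, participation ends after about 3.5 days, and the plan does not say whether surveys continue. This lowers capture in Group 1. Group 2 has no such rule. The documents do not settle the net sign.

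**5. What unequal capture would do (illustration only).** Expected recorded count = n × p × c. Here n = 110 ÷ 2 = 55 per group, from the planned sample and equal allocation. The true event rate p (20%, range 10% to 30%, same in both groups) and the captured share c are assumptions.

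- Equal capture, 50% in each: 55 × 0.20 × 0.50 = 5.5 recorded of 11 true events in each group. Fisher's exact test gives p < .05 in 2.0% of trials (0.9% to 2.5% over the range of p).
- Capture 70% in one group and 50% in the other: 55 × 0.20 × 0.70 = 7.7 against 5.5. At p = 10%, 3.85 against 2.75; at p = 30%, 11.55 against 8.25. Fisher p < .05 in 5.2% (2.0% to 8.0%).
- Capture 90% and 30%: 9.9 against 3.3. Fisher p < .05 in 37.4% (11.6% to 61.3%).

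Which group gets the higher count depends only on which is assumed better captured. The plan describes no such test.

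**6. Is item 12 consistent with the rest?** Item 12 does not expect adverse events; item 11 sets out what to do about deterioration, emergency care and hospitalization. Item 12 also makes an anticipated serious event reportable if it is at least possibly related and more frequent than expected. Applying that needs a count and an expected frequency, and the plan gives neither. Two review frequencies are named without saying which applies.

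**The case against.** The strongest reply is that this is a minimal-risk study in which both groups receive intensive in-home care from a clinical team, and that Group 2 is far from unobserved: it has calls after missed surveys, a six-week follow-up and a research-administered interview. Items 12 and 13 plan no by-group count, table or test of adverse events, so nothing in the plan would be distorted by unequal capture. The survey forms are not in the documents, and Table 1 has come through extraction in poor order. The sentence in item 12 might also be meant only for problems caused by the research.

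Much of this stands, and it rules out several stronger readings.

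- A reader might infer that Group 2 is reached only by monthly web surveys that ask nothing about events. The documents show more contact than that, and the content of the forms is inferred from a list of instruments.
- A reader might infer that events are found more often in Group 1, so that the device looks harmful. The termination rule works the other way, and no comparison is planned.
- A reader might build a ratio of observed events from the relapse rate in the Background (40% to 60% within 3 months). That figure is for patients treated for alcohol problems, not for people within a 52-week in-home program; relapse is not itself an adverse event; and any such ratio would simply be one assumed capture share divided by another.

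What the reply does not remove: no scheduled question is described, Aware care is not described as a route for reporting events to the study, and the shared contacts do not offset the extra rules in Group 1. If item 12 means only research-caused problems, it should say so.

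**Conclusion.** The point holds in a limited form. As written, finding adverse events depends on their reaching the PI, and the routes by which they can do so differ between the groups. Counts may be incomplete in both groups and may not be comparable between them. Neither the direction nor the size can be given from the documents; the counts in the illustration rest wholly on assumed event and capture rates. The conclusion assumes that Table 1 is a full list of what is asked. If the survey forms already contain an acute-care or serious-event item, the remaining task is to describe it in the protocol. Because the study is minimal risk and no by-group safety analysis is planned, this is a gap that should be closed, not a reason to hold the trial.

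**What to change.** Add the same fixed item to the month 1, 2, 3 and six-week assessments in both groups: any emergency visit, any hospital, detox or residential admission, or any other serious event since the last survey, with its date. This also supplies data for Aim 3.

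In item 12:

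- Name the item as the scheduled source of events, and record for every event how it was learned of.
- State that the PI continues to review all known events from every source. Restricting the review to the survey item would lose deaths and events in people who miss surveys.
- State that any between-group comparison rests on the common item, with events found only through missed-test calls shown separately.
- Reconcile the statement that adverse events are not anticipated with the emergency-room referral and hospitalization in item 11, and reconcile the two review frequencies.
- State whether participants terminated after missed tests are still asked the item. Without this, the common item does not cover them.

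The cost is one or two survey items (about a minute per assessment), some self-reported events to query, and a short amendment.
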